2.3.1.1.1 Thyroid-protection medication

Side effects of KI (potassium iodide) may include stomach or gastro-intestinal upset, allergic reactions, rashes, and inflammation of the salivary glands. In rare instances, it can cause "Iodism" (metallic taste, burning mouth and throat, sore teeth and gums, symptoms of a head cold, and sometimes upset stomach and diarrhea) or an allergic reaction can have more serious symptoms. These include fever and joint pains; swelling of parts of the body (face, lips, tongue, throat, hands, or feet); trouble breathing, speaking, or swallowing; wheezing or shortness of breath. Severe shortness of breath requires immediate medical attention.

2.3.1.1.2 Dose Limiting Toxicities (DLT) Probably Related to CLR 131

In this study, expected toxicities include febrile neutropenia, anemia, thrombocytopenia, and fatigue including, in some instances, Grade 3 and Grade 4. Per the CLR 131 Investigator Brochure, 90% of subjects are anticipated to have blood count recovery approximately 65 days after treatment with CLR 131. In this study, a DLT is defined as:

- Grade 4 neutropenia > 4 weeks
- Grade 4 anemia > 4 weeks
- Grade 4 thrombocytopenia > 4 weeks

- Grade 3 neutropenia > 8 weeks
- Grade 3 anemia > 8 weeks
- Grade 3 thrombocytopenia > 8 weeks

- Any other Grade 3 or 4 unexpected event at least possibly related to CLR 131

Growth factor support and blood transfusions are permitted in this study as clinically indicated by the treating physician.

Dose escalation will not be confirmed until all subjects in cohort recover to non-DLT levels or meet the criteria above.

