2.2 Rationale for a clinical study using CLR 131 in combination with EBRT

Locoregional recurrence in HNC represents a significant challenge. Approximately 50 % of HNC patients will experience loco-regional disease recurrence following initial therapy that commonly includes primary or postoperative radiation. Although some recurrent HNC patients can experience long-term tumor control following re-irradiation, this approach must be considered with great caution due to the risk of severe injury to normal tissue structures that maintain long-term recall from the prior radiation exposure.

Several studies have specifically examined the role of re-irradiation in HNC with general conclusions that there is considerable risk for high-grade toxicities (including death), but a defined opportunity for long-term survival (2 years) in approximately 10-20% of patients (A. M. Chen *et al.*, 2011; Dawson *et al.*, 2001; De Crevoisier *et al.*, 1998; Hehr *et al.*, 2005; Hoebers *et al.*, 2011; Kasperts *et al.*, 2005; Kramer *et al.*, 2005; Langer *et al.*, 2007; Mendenhall *et al.*, 2008; Nag *et al.*, 1998; Salama *et al.*, 2006; S. Spencer *et al.*, 2003; S. A. Spencer *et al.*, 2001; Stevens *et al.*, 1994).

Selection of patients who would most likely benefit from HNC re-irradiation remains an area of active investigation. Efforts to reduce the acute and long-term tissue injury profile by radiation with highly conformal techniques are clearly important in the retreatment setting. With the use of CLR 131, the dose of external beam radiation therapy can potentially be reduced or more precisely targeted, which serves to limit high dose radiation therapy to normal tissues in the head and neck.

The aim of this clinical trial is to evaluate the use of the novel radioisotope CLR 131 as a modality to provide "internal radiation" to recurrent disease in combination with EBRT. This combination regimen would be intended to provide definitive treatment of recurrent head and neck cancer by delivering radiation to HNC cells through CLR 131 uptake followed by the more traditional EBRT. We hypothesize that CLR 131 will reduce the overall dose of EBRT required for retreatment, and minimize the acute and long-term tissue injury that is commonly associated with standard reirradiation treatment plans.

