7.2.1.1 Treatment Dose Administration

Subjects who have uptake on SPECT/CT imaging scans are eligible for the treatment portion of the clinical trial. These subjects will be treated and evaluated as follows:

- Vital signs will be collected prior to and 1 hour post CLR 131 infusion
- On day 1 of the treatment period, CLR 131 will be administered through a freely running peripheral IV catheter via a slow infusion of approximately 30 minutes duration. The dose of CLR 131 will be calculated for each subject based on total BSA (not to exceed 2.5 m²) calculated from actual body weight and height at screening.
- SPECT/CT imaging will be performed on days 2, 3, 4-6, and 7-8.
- A second treatment dose of CLR 131 will be given on day 8.
- CBC with differential and serum chemistries weekly for 12 weeks (beginning at day 1 of first treatment dose)

- Confirm subject is taking thyroid protection medication as directed.
- Adverse event evaluation
- Urine pregnancy test for WOCP (within 24 hrs prior to each CLR 131 dose)

7.2.1.2 External beam radiation therapy (EBRT) (approximately 7-14 days after the last CLR 131 treatment dose)

Based on the calculated absorbed dose of CLR 131 to the specific targeted tissue, the subject will undergo standard of care EBRT to complete the designated radiation dose outlined in the re-irradiation plan.

An EKG will be performed on the first day of the SOC EBRT. During the course of EBRT, subjects will be evaluated for any adverse events.

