11.3 Characteristics of an Adverse Event

11.3.1 Relationship to Study Intervention

The PI will determine the relationship of adverse events to the research intervention using the following scale:

- Definite = AE is definitely related to the study procedures
- Probable = AE is likely related to the study procedures
- Possible = AE is possibly related to the study procedures
- Unlikely = AE is doubtfully related to the study procedures
- Unrelated = AE is definitely not related to the study procedures

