Resulting in hospitalization \geq 24 hrs	10 Calendar Days	24 Hour; 5 Calendar Days
Not resulting in Hospitalization \geq 24 hrs	Not required	

***Planned hospitalizations for disease-related surgery, routine procedures (such as G-tube placement), non-disease-related procedures, and inpatient hospitalization for radiation protection/exposure levels are not considered SAEs. A hematologic adverse event grade 1-4 will not be defined as an SAE if it can be managed with blood product transfusions, unless it exceeds the window for a dose limiting toxicity.**

Expedited AE reporting timelines are defined as:

- **24-Hour; 5 Calendar Days** – The AE must initially be reported within 24 hours of learning of the AE, followed by a complete expedited report within 5 calendar days of the initial 24-hour report.
- **10 Calendar Days** – A complete expedited report on the AE must be submitted within 10 calendar days of learning of the AE.

Serious adverse events that occur more than 28 days after last EBRT treatment or 85 days after first treatment dose of CLR 131, whichever is later and have an attribution of possible, probable, or definite require reporting as follows:

Expedited 24-hour notification followed by complete report within 5 calendar days for:

- All Grade 3, 4, and 5 AEs

Expedited 10 calendar day reports for:

- Grade 2 AEs resulting in hospitalization or prolongation of hospitalization

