11.5 Halting Rules

During the conduct of this study, adverse events and serious adverse events that are categorized as probably related to CLR 131 will be evaluated and analyzed weekly by the principal investigators. If >25 % of subjects have serious adverse events that are probably related to CLR 131 treatment, then enrollment for the study will be suspended for further analysis.

Subsequent review of serious, unexpected, and related AEs will be evaluated by the DSMC, IRB, Collectar Biosciences. Collectar Biosciences and local regulatory authorities retain the authority to suspend additional enrollment and administration of CLR 131 for the entire study, as applicable.

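### The DLT definition stops at Grade 4, so some deaths at least possibly related to CLR 131 stay out of the Table 3 count; at Dose Level 2 one such death reads 0/4 (expand) instead of 1/4 (stay)

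*Combined protocol and SAP*

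**What the plan says.** **DLT definition (Section 2.3.1.1.2).** Grade 4 neutropenia, anemia or thrombocytopenia counts if it lasts more than 4 weeks, and Grade 3 if it lasts more than 8 weeks. The last line is "Any other Grade 3 or 4 unexpected event at least possibly related to CLR 131". The same section lists febrile neutropenia, anemia, thrombocytopenia and fatigue as expected, in some instances at Grade 3 or 4.

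**Hold (Sections 2.3.1.1.2 and 14.2).** "Dose escalation will not be confirmed until all subjects in cohort recover to non-DLT levels or meet the criteria above".

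**Dose decisions (Section 14.2).** Table 3 counts subjects with DLTs and is read at 4 and 8 treated. At 4 treated, 0 is E, 1 is S, 2 is D, and 3 or 4 is DU. A 0/4 result at Dose Level 2 leads directly to expansion. At most 8 subjects are treated per level during escalation (with one exception at Level 1), and up to 12 at the MTD.

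**Grade 5 elsewhere.** Section 11.4.2 has a reporting column for Grades 3 to 5, and its rule for late events covers "All Grade 3, 4, and 5 AEs".

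**Halting rule (Section 11.5).** Adverse events "categorized as probably related to CLR 131 will be evaluated and analyzed weekly by the principal investigators". The numerical trigger for suspending enrollment is worded as follows: "If >25 % of subjects have serious adverse events that are probably related to CLR 131 treatment". The attribution scale in Section 11.3.1 has a separate category below probable: "Possible = AE is possibly related to the study procedures".

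**Analysis and status.** Section 14.2 bases outcome analysis on subjects treated at the MTD, and Section 14.3.1 tabulates adverse events with exact intervals. The Protocol Summary records the last DLT window as completed on June 16, 2022.

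**The concern.** The MTD rests on the Table 3 count, and the definition feeding that count omits the worst grade. Death is foreseeable here: Section 2.2 says that re-irradiation carries "considerable risk for high-grade toxicities (including death"). That remark concerns re-irradiation rather than CLR 131, but EBRT starts "approximately 7-14 days after the last CLR 131 treatment dose" (Section 7.2.1.2), so after that point both treatments are candidate causes and an attribution of only possible is plausible.

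The decision most exposed is the one at Dose Level 2. A reading of 0/4 opens expansion to as many as 12 − 4 = 8 more subjects at that dose, and Section 14.2 requires no further Table 3 reading on the way. A reading of 1/4 requires a second cohort of four and a reading at 8.

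**Working it through.** **1. Which related deaths are uncounted.** Apply the seven DLT lines to a death at least possibly related to CLR 131:

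| Course before death | Result under Section 2.3.1.1.2 |
|---|---|
| A recorded unexpected Grade 3 or 4 event, at least possibly related | Counted, through the last line |
| Graded only as Grade 5 | Not counted: no line names Grade 5 |
| Expected Grade 3 or 4 cytopenia or febrile neutropenia, death before the 4- or 8-week limit | Not counted: duration not reached, and the Grade 3 or 4 event was expected |

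Section 11.3.2 makes an event unexpected if its severity exceeds the described risk. A fatal cytopenia would qualify as unexpected, but the last line still covers only Grades 3 and 4.

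**2. Table 3 reproduced.** Inputs from Section 14.2: target 0.2 and both epsilons 0.1, so the stay interval is (0.1, 0.3). Assumed, because not stated: uniform prior, and exclusion of a dose when P(p > 0.2) exceeds 0.95. The posterior is Beta(1 + x, 5 − x) at n = 4. Each interval's probability is divided by its length, and the largest value decides.

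- x = 0: E (0.59049 removed from 1, over 0.1) = 4.095; S (0.59049 − 0.16807)/0.2 = 2.112; first D interval (0.16807 − 0.03125)/0.2 = 0.684. Decision E.
- x = 1: E 0.08146/0.1 = 0.815; S (0.47178 − 0.08146)/0.2 = 1.952; first D interval (0.81250 − 0.47178)/0.2 = 1.704. Decision S.

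All of columns 4 and 8 match Table 3. The only cell in the whole table that differs is 1/1 (D printed, DU computed), which cohorts of four never use.

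**3. Effect at Dose Level 2, with no other DLT.** One uncounted death: 0/4 (direct expansion) as written, 1/4 (S) if counted. Two: 0/4 as written, 2/4 (D) if counted. For one death the posterior mean DLT rate moves from 1/6 = 0.167 to 2/6 = 0.333, and P(p > 0.2) from 0.33 to 0.74.

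**4. What the skipped reading could have shown.** From 1/4, Table 3 de-escalates at 3/8 or more, so at least 2 DLTs are needed in the next 4. P = 1 − (1 − r)^4 − 4r(1 − r)^3 for an assumed true DLT rate r:

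- r = 20%: 1 − 0.4096 − 0.4096 = 18.1%
- r = 30%: 1 − 0.2401 − 0.4116 = 34.8%
- r = 40%: 1 − 0.1296 − 0.3456 = 52.5%

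**5. Does the percentage halting rule catch it?** If the death is judged only possibly related, it never enters the count. If judged probably related, assume a running count of treated subjects, each event being assessed before the next subject is dosed.

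- Among the first four subjects, one event trips the rule at 1/1, 1/2 or 1/3, but not at 1/4 = 25%.
- After four Level 1 subjects with no such event, one event at Level 2 gives 1/5 = 20% down to 1/8 = 12.5% and never trips it.
- Two Level 2 events trip it at 2/6 = 33.3% or 2/7 = 28.6%, but not when the second is in subject 8 (2/8 = 25%), which is 3 of the 6 possible pairs.

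**6. How often it could matter.** The documents give no rate of related death, so q per subject is assumed. If every related death were of the uncounted kind, the chance of at least one in 4 is 1 − (1 − q)^4. If all are also judged probably related, the chance that this happens with the halting rule silent, after a clean Level 1, is 4q(1 − q)^3 + 3q²(1 − q)². The last two columns give the fall in P(0/4) when deaths are counted, (1 − d)^4 − (1 − d − q)^4, for an assumed non-fatal DLT rate d:

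| q | At least one in 4 (upper bound) | Halting rule silent | Fall, d = 10% | Fall, d = 20% |
|---|---|---|---|---|
| 1% | 3.9% | 3.9% | 0.656 − 0.627 = 0.029 | 0.410 − 0.390 = 0.020 |
| 5% | 18.5% | 17.8% | 0.656 − 0.522 = 0.134 | 0.410 − 0.316 = 0.093 (unrounded) |
| 10% | 34.4% | 31.6% | 0.656 − 0.410 = 0.246 | 0.410 − 0.240 = 0.169 (unrounded) |

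**The case against.** The best counter-case has four parts.

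**A related death would not pass unseen.** This is correct. Unexpected and possibly related harm can be an unanticipated problem reportable to the IRB, the DSMC and the IND holder (Sections 11.1.1 and 11.4.1). Grade 5 serious events carry a 24-hour initial report (Section 11.4.2). The second paragraph of Section 11.5 provides for review of serious, unexpected, related events without a threshold of probable, and lets the IND holder suspend enrollment and dosing. Section 12 adds regular team and DSMC review. All of these act by judgement, however, and none alters the Table 3 count.

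**The hold may cover the move to expansion.** In Section 14.2 it stands immediately before the 0/4 rule for Level 2, and the protocol also uses dose escalation as the name of the phase that sets the MTD. That reading is fair. It still does not settle the count: a subject who dies may neither recover nor meet a listed criterion, and no text says how to classify that subject.

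**The gap is narrower than all related deaths.** This stands. A reader might infer that every related death escapes Table 3. The documents do not support that, because a death preceded by a recorded unexpected, possibly related Grade 3 or 4 event already counts.

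**The death would be reported with the MTD.** This also stands for the main scenario. A reader might infer that the death would vanish from the results. If Level 2 becomes the MTD, the subject is in the MTD analysis set of Section 14.2 and in the adverse-event table of Section 14.3.1. What that table would not show is a death at a non-MTD level, if the Section 14.2 restriction is applied despite the wider safety set in Section 5.5.1, or whether the dose decision would have differed.

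The study team may well have meant Grade 3 or higher and would probably have treated a related death as dose-limiting. The text does not require it.

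**Conclusion.** The point holds in this limited form: two kinds of related death (graded only as Grade 5, or following an expected cytopenia or febrile neutropenia too early for the duration lines) are not DLTs as written. At Dose Level 2 one of them turns stay into direct expansion. This is a stated rule that gives the wrong count, and it is worth correcting.

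The change from 0/4 to 1/4 needs no assumption beyond the text and the absence of another DLT in the cohort. The 3.9% to 34.4% range does rest on assumptions: related-death rates of 1% to 10% that no document supplies, and every such death being uncounted. It is an upper bound and not an estimate. The halting-rule results for probably related events also assume a running denominator, which Section 11.5 does not specify.

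A reader might go further and infer that this trial's MTD is wrong. Nothing in the documents says that a related death occurred, and with the DLT window closed no past escalation decision can change.

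**What to change.** 1. **Definition.** In the last DLT bullet of Section 2.3.1.1.2, insert *or any Grade 5 event* after the Grade 3 or 4 unexpected event, set off by commas so that the existing relatedness condition governs both. A related death then meets the criteria, which also settles how the hold treats it. The cost is five words. For this trial the change matters only if dosing reopens or the definition is reused.
2. **Reporting.** Add to Section 14.3.1 a short table by dose level, in the Section 5.5.1 safety set, with two counts: protocol DLTs, and Grade 5 events at least possibly related to CLR 131. State whether counting the second changes any Table 3 decision. If there were no such deaths, one sentence is enough. The data are already collected. The table adds deaths at non-MTD levels and the effect on the MTD decision; its one drawback is that it may make the declared MTD look less favourable.

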2.3.1.2 External beam radiation therapy (EBRT)

Radiation side-effects in the treatment of head and neck cancer are well known. Though subjects for this trial will be given EBRT as part of standard of care, we are listing the side effects here to distinguish from those that are expected as part of CLR 131 administration.

Common side effects include: mucositis, difficulty swallowing which may necessitate a feeding tube, dry mouth, change in taste and smell, reduced saliva production, hoarseness, radiation dermatitis, ear pain/infection, hearing loss, fatigue, weight loss, dehydration requiring IV fluids and electrolyte replacement, hair loss, tooth decay, decreased thyroid function. Rare and serious side effects include: breathing and swallowing issues that require a tracheotomy, nerve damage in the head and neck region, radiation necrosis of the jaw, damage to the larynx or nerves, damage to the skin, soft tissues or other parts of the head and neck that may require a surgery to correct and damage to the spinal cord which may cause permanent weakness.

2.3.1.3 Modified Barium Swallow (MBS) Studies (standard of care)

To minimize risk, the procedure has been carefully planned. Radiation dose received during a MBS (between 0.2 and 0.85mSv) is lower than doses received from other common fluoroscopic and interventional radiology procedures. The risk of developing a fatal cancer from a MBS is 1 in 39,000. Occasionally, patients may be allergic to the flavoring added to the barium. There is a slight chance that barium could be retained in the gastrointestinal (GI) system, leading to a blockage. Women should inform their physician or x-ray technologist if there is any possibility that they are pregnant.

2.3.1.4 Single photon-emission computed tomography (SPECT) /CT

There is no additional risk associated with SPECT acquisition. However, a low-dose spiral computed tomography (CT) scan will accompany every SPECT acquisition for attenuation correction, anatomical conformation and dosimetry. The effective radiation dose associated with the low-dose spiral CT scan will differ with each individual; however, for the purposes of this study population we anticipate radiation exposure from CT scans to be ~1.5 mSv/scan (maximum total radiation from 5 scans would be ~7.5 mSv). For comparison, estimates for natural background radiation in the United States (vary based on location) is ~3.1 mSv/year.

2.3.1.5 Other risks from study-related procedures

- Blood draws for clinical laboratory testing: bruising, swelling at the injection site, dizziness and lightheadedness

- Saliva and oral swab collection: dry mouth (expected to resolve within a few minutes following collection)
- Maximum expiratory pressure (MEP) and voluntary cough: subject may feel slightly out of breath immediately following the measurement (expected to resolve within a few minutes of procedure).
- Maximum lingual pressure: subject may experience discomfort or soreness of the tongue measurement (expected to resolve within a few minutes of procedure).
- Questionnaires: risk of loss of confidentiality is possible but not likely with data security safeguards in place.

2.3.2 Potential Benefits

There is no known benefit to subjects' participation in this study. While there is hope that a subject's cancer will respond to treatment with CLR 131, there is no proof of that at this stage. There is no standard treatment regimen for patients with locoregionally recurrent head and neck cancer, and thus re-irradiation with EBRT can be considered for patients in order to provide long term disease control. However, patients who undergo re-irradiation for recurrent disease experience significant toxicities and side effects. Thus, patients with locally recurrent head and neck cancer have an unmet need for treatment options with acceptable side effects and toxicities. This study is likely to yield knowledge about the use of CLR 131 in treating head and neck cancer when combined with external beam radiation, which could help future patients.

3 OBJECTIVES

3.1 Study Objectives

3.1.1 *Primary Objective*

- To evaluate the safety and tolerability of CLR 131 in combination with EBRT in subjects with recurrent cancers of the head and neck

3.1.2 *Secondary Objectives*

- To perform dosimetric evaluation of CLR 131 in subjects with recurrent cancers of the head and neck
- To assess tumor response following treatment with CLR 131 in combination with external beam radiation therapy
- To evaluate changes in swallowing function before and after treatment with CLR 131 in combination with external beam radiation therapy
- To evaluate changes in quality of life before and after treatment with CLR 131 in combination with external beam radiation therapy
- To evaluate salivary flow rate before and after treatment with CLR 131 in combination with external beam radiation therapy

3.2 Study Outcome Measures

3.2.1 *Primary*

- Incidence of adverse events assessed using Common Terminology Criteria for Adverse Events (CTCAE) version 5.0

3.2.2 *Secondary*

- Median radiation treatment time and median number of dose delays due to toxicity
- CLR 131 tumor uptake via SPECT/CT imaging and Monte Carlo calculations
- Overall response rate (ORR) defined as the proportion of subjects who experience either a partial response or complete response within 6 months post completion of EBRT as measured by standard of care imaging (e.g. CT, MR, PET-MR)
- Swallow function assessed by Dynamic Imaging Grade of Swallowing Toxicity (DIGEST) scale
- Quality of life (QoL) assessed by MD Anderson Dysphagia Inventory score (MDADI)
- Salivary flow rate related quality of life assessed by stimulated salivary flow

